### Nortriptyline

Smokers assigned to the Nortriptyline Group will receive a 12-week regimen of nortriptyline. Medication administration procedures will be similar to those used by Hall et al. in one of the first randomized clinical trials using nortriptyline for smoking cessation. Ten days before their target quit day and following the baseline startle assessment, smokers in this group will receive 25 mg/day of nortriptyline for three days. Medication dose will then be increased to 50mg (25 mg bid) for four days. Serum levels will be assessed at the end of the first week of medication (3 days before quitting) and the dosage will be increased to a maximum of 50 mg bid if plasma concentrations do not reach the recommended therapeutic range (between 50 and 150 ng/mL). Blood samples will be drawn again at week 4 (5 days after quitting) of the medication and dosage will be adjusted again and checked the following week if necessary. The modal dose in the Hall study was 100mg/day. Participants will remain on the adjusted dose until the eleventh week of medication when the dosage will be tapered to 50 mg/day.

### Placebo

Participants in the placebo group will receive a total of 12 weeks of placebo plus the behavioral counseling described above. All other assessment procedures will be identical to the other groups.

### Medication Blinding

Medications will be supplied by the Drug Product Services Laboratory in the Department of Clinical Pharmacy, University of California, San Francisco (see letter of support section I). This pharmacy made the nortriptyline and bupropion placebo preparations used in [name] nortriptyline and bupropion research studies and has agreed to provide our study with similar preparations. To keep all medications similar in appearance, active and placebo formulations will be enclosed in unmarked sealed and brushed capsules and shipped to MD Anderson Department of Experimental Therapeutics Research Pharmacy for patient distribution. The MD Anderson pharmacy will implement the randomization schedule as developed by the study statistician. Because nortriptyline levels can only be detected in the nortriptyline group, only the study

physician (and his staff) will be un-blinded as to treatment condition, as they will be responsible for the dose titration and medication checks. Our study physician will not be involved in the counseling or startle assessments and he or a member of his staff will conduct the adverse reports assessments. All other members of the research team will remain blind to treatment condition.

To maintain the integrity of the blind among the participants themselves and the other research staff, about 10% of all participants in the placebo and bupropion groups will also undergo the same schedule of blood analysis as the nortriptyline group. We feel this is an appropriate compromise to maintain a blinded research protocol and at the same time, minimize the risk of unnecessary blood draws among the bupropion and placebo groups. The code for who will be selected for the blood draw will be imbedded in the randomization schedule. Medication will be un-blinded in the event of drug related a serious adverse event, Abstinence Compliance and Startle Assessments

[figure not shown]
As shown in **Table 2**, compliance with abstinence requirements will be checked at the beginning of each laboratory session, all telephone counseling sessions, and each in-person counseling session that does not coincide with a laboratory startle assessment. Abstinence at each startle assessment will be defined in two ways. The first will involve stringent criteria of no smoking (not even a puff) from the target quit date to the day of each post-quit startle assessment plus a corresponding expired CO of <8ppm. Less stringent criteria of abstinence will also be applied to evaluate the effects of the quit attempt among all smokers, even those who do not meet the stringent criteria of abstinence as defined above. The less stringent criteria will be as follows: (1) Abstinence prior to the first post-quit startle probe assessment (2 days post-quit) be defined as a self-report on the SSQ of being abstinent on their quit date, and smoking no cigarettes at least 24 hours prior to the assessment plus a current CO <8ppm. (2) For the time period encompassing the 5 and 28 days post-quit startle assessments, abstinence will be defined by the following conditions (a) abstinence on the quit date; b) abstinence at the first post-quit assessment; c) self-report of abstinence at the 5 and 28 day post-quit laboratory assessments with corresponding CO levels <8ppm, and (c) having smoked no more than 1 cigarette, between the 2 and 5 day assessments, and no more than 2 cigarettes in the 4 weeks between the 5 and 28 day post quit laboratory assessments. Our data will be analyzed using both criteria to evaluate abstinence. We took a similar approach in our preliminary studies and saw no differences in the startle comparisons between abstainers defined by either the more or less stringent criteria, although both were different from controls. Participants who are not abstinent on the quit day or prior to the 2nd laboratory session (by the less stringent standard) will not undergo the 2nd laboratory assessment procedure at their originally scheduled time. Within the context of their scheduled counseling, these smokers will be provided with support and given an additional opportunity to abstain from smoking for a 2 day period as called for in the first startle assessment. Participants who fail a second time or who relapse after their 2nd laboratory session (using the less stringent criteria described above) will continued to be counseled to quit and will be evaluated on the same schedule of laboratory assessments as the abstainers. Our preliminary data clearly show that these, “never quitters”, or “relapsers”, both significantly reduce their smoking and experience a substantial increase in negative affect and startle reactivity as a function of nicotine withdrawal. Thus even though some smokers may not quit entirely, they experience considerable distress and do not return to baseline levels of smoking, at least for the period in which the behavioral counseling is provided. In our preliminary studies and in the current study the counseling is coincident with the startle assessments and is designed to encourage continuous quitting activity even if they initially fail. Hence, as described in our preliminary studies we will analyze our startle data using models that both separate and combine relapsers and never quitters. This analytic strategy will maximize the information gained from this experiment.

Based on our preliminary data about 25%-50% of the participants may fail to achieve abstinence/maintain abstinence after their quit date, using only the behavioral counseling provided. Our preliminary studies are not yet complete and our abstinence rates have ranged been as high as 75% at other times when we have undertaken interim analysis. To enhance abstinence rates in the present study, we have both increased the counseling frequency, in comparison to our previous study, and provided a monetary bonus for abstinence. With these adjustments, we feel it is reasonable to expect 60%-75% of those in the placebo group (counseling alone) will be abstinent at the 28-day post-quit assessment. Based on the initial clinical trials with both drugs, we expect 75%-80% of those in both drug groups to have achieved abstinence by day 28 post-quit. Our power calculations for interactions involving abstinence status, treatment and genotype have

taken this range of abstinence into account (see page 29). We have also outlined a strategy for comparing all participants in the drug treatment groups to placebo, similar to those we conducted between the Quit and Control groups in our preliminary studies. This approach is outlined in our data analysis section, along with our plan to evaluate differences in abstinence status between and within groups.

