### Adverse Event Monitoring & Concomitant Medication

At each of post-baseline laboratory and in-person counseling session, participants will be assessed for side effects and concomitant medications using standard FDA guidelines recommended for these two procedures. Adverse events will be reviewed by our study physician who will recommend changes in dosage or other clinical intervention as appropriate for the event. Adverse event monitoring will continue up to 30 days after medication is completed, or longer if on going events are observed.

**Genotyping** Eligible volunteers will be asked to provide a blood sample during the orientation visit for conducting genetic analyses. Genotyping assays are described in the **Appendix 4** and summarized below. Genomic DNA will be extracted from each coded blood sample for polymerase chain reaction (PCR) analyses using standard phenol extraction methods.

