### Bupropion

Smokers in the Bupropion Group will receive a 12-week regimen of bupropion (150 mg q AM for three days; 150 mg b.i.d. thereafter). Bupropion has been used effectively for smoking cessation in regimes ranging from 7-12 weeks. Our procedures will closely resemble those used in earlier trials. Participants will begin bupropion on the day they attend their baseline laboratory session (10 days before the target quit day), but after the session is completed. Bupropion will be tapered to 150 mg/day one week before the conclusion of the regimen.

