#### Adverse Experiences Associated with Bupropion Use

Comprehensive screening will be conducted to ensure that all participants with contraindications for bupropion use (e.g., current or prior diagnosis of seizure disorder, current or prior diagnosis of bulimia or anorexia nervosa, concomitant use of monoamine oxidase inhibitors or other bupropion products, and hypersensitivity to bupropion) are excluded from participation. The most commonly adverse experiences associated with bupropion use are dry mouth and insomnia. Other frequent adverse experiences may include asthenia, headache, dyspepsia, flatulence, vomiting, agitation, irritability, sweating, and urinary frequency. Adverse effects and concomitant medications will be assessed at each of the post-baseline laboratory and counseling session. Participants' blood pressure will also be measured at each of laboratory assessment. The study physician will monitor participants' complaints of adverse events and, when necessary, adjust the dosage or discontinue medication. Adverse experiences and medication assessments will continue until completion of the regimen (day 84 of the program).

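### The study physician and his staff are unblinded to treatment without limit, although the stated reason needs only nortriptyline or not; adverse event collection and treatment changes in bupropion versus placebo are left open to avoidable bias

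*Combined protocol and SAP*

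**What the plan says.** Medication Blinding gives one reason for unblinding anyone, namely that serum nortriptyline will be measurable in one arm alone. On that ground the "physician (and his staff) will be un-blinded as to treatment condition, as they will be responsible for the dose titration and medication checks". The disclosure is of treatment condition as such, with no restriction to nortriptyline or not. The same section says of the physician that "he or a member of his staff will conduct the adverse reports assessments". It also keeps him out of counseling and the startle sessions, and keeps the rest of the team blind.

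Adverse Event Monitoring & Concomitant Medication schedules adverse event checks at every post-baseline laboratory session and in-person counseling session, for all participants, and states: "Adverse events will be reviewed by our study physician who will recommend changes in dosage or other clinical intervention as appropriate for the event". The section on adverse experiences with bupropion has the physician monitor "complaints of adverse events and, when necessary, adjust the dosage or discontinue medication". The nortriptyline section repeats this wording. Neither gives criteria.

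On dosing, the Nortriptyline section ties the dose to serum level: "the dosage will be increased to a maximum of 50 mg bid if plasma concentrations do not reach the recommended therapeutic range". The Bupropion section sets a "12-week regimen of bupropion (150 mg q AM for three days; 150 mg b.i.d. thereafter", with a scheduled taper at the end and no level check. The Placebo section describes no titration.

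**The concern.** The unblinding is wider than the reason for it. Titrating nortriptyline requires knowing who is on nortriptyline. It does not require knowing which of the others are on bupropion and which on placebo. Yet the people told this are the ones who elicit complaints in those two arms, and one of them acts on the complaints.

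The judgment involved is not mechanical. Insomnia and irritability appear in the protocol both as nicotine withdrawal effects and as adverse experiences of bupropion. Every participant is asked to quit, so the same complaint can come from either arm. Whether it is put down to drug or to withdrawal, how far it is probed, and whether medication is changed can all be influenced by knowing the arm.

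At stake are the even-handedness of adverse event collection and of dose changes and stopping between bupropion and placebo. At one remove, so is the treatment actually received in that contrast.

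**Working it through.** There is no plan figure to reproduce. The check is a comparison of sections, with one headcount for scale.

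**1. What titration needs, arm by arm.**

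| Arm | Routine dosing | Level-driven titration? | Must the titrating staff know the arm? |
|---|---|---|---|
| Nortriptyline | Stepped, then set by serum level | Yes | Yes: nortriptyline or not |
| Bupropion | Preset schedule and taper | None described | Only that it is not nortriptyline |
| Placebo | 12 weeks of placebo | None described | Only that it is not nortriptyline |

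The stated reason therefore supports a yes/no disclosure. No section gives a reason for the bupropion/placebo distinction.

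**2. Who does what with the knowledge.**
- Collecting adverse events: the physician or a member of his staff (Medication Blinding). Both are unblinded.
- Reviewing events, adjusting the dose and stopping medication: the physician (Adverse Event Monitoring, and the bupropion and nortriptyline adverse experience sections).
- Counseling, startle assessment and everything else: the rest of the team, who stay blind.
- No blinded adverse event assessor and no blinded stopping decision is described.

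**3. Can treatment changes come before the startle sessions?** Medication starts after the baseline session, 10 days before the quit date. Counseling is spread over the 38 days of the program (10 + 28 = 38), with two in-person sessions before quitting. Arm-aware changes could therefore precede the day 2, 5 and 28 sessions. That establishes opportunity, not occurrence.

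**4. Scale.** The sample is 354 in three arms; the allocation ratio is not stated.
- Equal allocation: 354 / 3 = 118 per arm; 2 × 118 = 236 on bupropion or placebo.
- In general the number is 354 minus the size of the nortriptyline arm. If nortriptyline took half the sample (177), it would be 177. If it took a quarter (88.5), it would be about 266.

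This counts the participants whose arm is disclosed without a titration need. It does not measure bias. The documents give no expected adverse event or stopping rates, so no size or direction can be derived.

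**5. What the plan already has.** Active and placebo capsules are made to look alike. The research pharmacy runs the randomization schedule, and the code for the decoy blood draws is embedded in that schedule. About 10% of bupropion and placebo participants have such draws to protect the blind (0.10 × 236 = 23.6, about 24 with equal arms). A restricted release of codes fits this arrangement.

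**The case against.** The strongest reply is that this is a disclosed choice with its reason given, and that the outcome is protected. Blink responses are scored by acquisition software, the physician takes no part in startle or counseling work, and the rest of the team is blind. Participants are compared by assigned Group. Nothing says that stopping medication ends laboratory assessments or removes anyone from the mixed models. All of this stands. A reader might infer that unblinded staff being present around startle visits biases the startle measure, but the documents do not support that. The sentence keeping the physician out of startle work does not name his staff, but no section gives them a startle role.

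Other stronger inferences also fail:
- **That a planned safety comparison is compromised.** The Data Analysis section contains no formal between-arm test of adverse events or of stopping.
- **That the whole unblinded group decides on stopping.** Only the physician is given that role; his staff may collect reports.
- **That unblinding for a drug-related serious adverse event is redundant.** It serves everyone still blinded, participants included. The sentence also breaks off in the available text, so its full scope cannot be judged.

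Two further objections have some force. The stated reason includes medication checks, a term left undefined, and the bupropion section allows the physician to "adjust the dosage or discontinue medication", so some dose management is foreseen in that arm. Neither passage says that telling bupropion from placebo is necessary for it. Second, narrowing the disclosure protects only one of the three pairwise comparisons. That is true, but the nortriptyline exposure follows from titration, and the bupropion/placebo exposure does not.

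**Conclusion.** The point holds as an avoidable weakness in blinding, limited to adverse event ascertainment and treatment changes in bupropion versus placebo. With equal allocation, which is an assumption, about 236 of 354 participants are concerned. Any effect on Hypotheses 1 and 2 would be indirect, through treatment received, and cannot be quantified. It should not be read as evidence that the startle results would be biased.

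The conclusion rests on taking the unqualified reference to treatment condition at face value. The protocol does not list arm by arm what is disclosed. If a narrower disclosure is intended, saying so would settle the matter. The change is worth making because the plan gives up a blind that it states no need to give up, and keeping it costs little.

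**What to change.** Amend Medication Blinding so that the research pharmacy releases to the study physician and his staff only nortriptyline status (yes or no) and the level results, and state that bupropion versus placebo stays concealed from them.

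The unblinding provision is at present stated only for drug-related serious adverse events, whereas Adverse Event Monitoring and the two adverse experience sections have the physician managing ordinary complaints. The sponsor should reconcile these passages and state how individual unblinding would work. No dosing or stopping rule needs to change for this.

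The cost is a restricted code list at the pharmacy and a short edit to the protocol; no extra staff or visits are needed. There are two downsides. The physician would need individual unblinding where the arm matters for a participant's care. Nortriptyline versus either other arm would also remain unblinded to these staff.

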**Figure 7. Laboratory Protocol**

Abstinence compliance following startle assessments (28 days post quit).

As shown in Table 2, we will assess abstinence and days to relapse using a telephone SSQ interview administered at 2 and 4 months post-quit and at the 3 and 6 month post-quit follow-up points. Participants will have completed the medication regime 10 days prior to the 3-month follow-up. Abstinence from the phone interviews will be verified using return mail cotinine. At the 3 and 6 months follow-up, abstinence will be verified by expired CO (<8ppm) obtained in the clinic. Cotinine will also be assessed at follow-up to provide a measure of tobacco exposure among those who fail to quit. For of these assessments, relapse will be defined in two ways: 1) using the traditional 7-day point prevalence criteria at each assessment (no smoking not even a puff in the 7 days prior to the assessment) and 2) using the recently developed guidelines from the SRNT committee on measurement of abstinence, which defines relapse as having smoked for 7 consecutive days, or, a puff a week for 2 consecutive weeks, beginning 2 weeks after the target quit date.

We recognize that the telephone interviews described for the 2 and 4 months post-quit time points may seem redundant with the 3 and 6 months follow-ups, that are more typical of a clinical trial. However, this study is not exclusively a treatment outcome comparison in which abstinence rates at 6 months are the only focus. A primary dependent variable in this study is the *number of days* to relapse in relation to startle responding and we feel it is appropriate to assess abstinence status more

often in order to better capture this data. Participants who report abstinence in these telephone assessments will be asked to provide a saliva cotinine sample using a mail kit developed for a current clinical trial. Participants will also be paid \$5 for each saliva sample provided. The procedure of having participants provide saliva samples by mail has worked successfully in previous studies conducted by our group. We have had few problems using the mail-in cotinine procedure in our current trial. Experience in our current trial, suggests that participants become very familiar with the salivette collection procedure since it is used in prior clinic visits. The kits contain a Teflon strip to stimulate saliva production, a cotton dental roll which is placed in the mouth for 30-45 seconds (until well saturated), a salivette collection tube to retain the dental roll after use, and a self-addressed bio-container envelope with pre-paid postage for over-night mail.

### Laboratory Startle Assessment Sessions

The protocol for the individual laboratory startle assessments will be similar for all four sessions, and is described in **Figure 7**. Each laboratory session will begin at approximately the same time of day for each participant (10-11am). Participants will be asked to limit their intake of coffee (or equivalent) to no more than 1 cup prior to 8:00 am on the day of each laboratory session. Smoking for all groups will be unrestricted prior to

the first (baseline) laboratory assessment session. The first session will be used to assess normal startle responses to affective stimuli prior to any nicotine deprivation or pharmacological treatment. Subsequent sessions will be used to assess the effects of treatment modality (nortriptyline, bupropion, placebo) and genotype on startle responses to affective stimuli during the 28 days following the quit attempt. The target days for these assessments are 2 days post quit (range 1-3 days); 5 days post (range 3-5) and 28 days post-quit (range 26-30). Ranges are provided as in our preliminary studies to accommodate scheduling changes resulting from missed visits or a repeat visit 2 (see abstinence criteria). Moreover, we have extended our final session from 10-14 days in our preliminary study to 28 days in the current proposal to more readily capture medication effects on startle responding about midway through drug treatment and towards the end of the 30-day withdrawal period.

At the beginning of each laboratory session, participants will be asked to complete the WSWS, CES-D, and PANAS, as described above. At the baseline session all participants will be instructed to smoke one cigarette after completing these instruments, to ensure similar conditions of non-deprivation preceding the startle probe trials. This is similar to the procedure used by Tiffany and colleagues and is identical to the baseline session described in our preliminary study.

Within each of the four sessions, smokers will be exposed to 48 startle probe trials. Each trial will involve the presentation of a picture with either positive, negative, neutral emotional content, or a smoking cue, while an acoustic stimulus is administered. Each startle probe trial will involve the assessment of eye-blink magnitude.

